#### **12.4.3. Exploratory Endpoints**

- Severity of radiation esophagitis-related pain, dysphagia, and dyspepsia during combined chemotherapy and RT using these fields of the NCI PRO-CTCAE weekly during treatment, and 4 weeks after completion of chemoradiotherapy;
- Incidence of acute esophagitis  $>$  Grade 2 through 4 weeks after completion of chemoradiotherapy, using the RTOG scale;
- Incidence of acute severe (Grade 3-4) radiation esophagitis through 4 weeks after completion of chemoradiotherapy, using the RTOG scale;
- Patient-reported dysphagia via a daily patient log and need for parenteral or tube feeding;
- Opioid use by collecting the patient's analgesic/narcotic use in the previous 24-hour period at each weekly evaluation.

#### **12.5. Safety Analysis**

Adverse events will be grouped by system organ class, high level term, and preferred term according to the Medical Dictionary for Regulatory Activities (MedDRA) dictionary. Incidence by subject will be tabulated for all treatment emergent, serious, severe, and treatment-related AEs. Detailed listings will be provided for all SAEs, deaths, and withdrawals due to AEs.

Laboratory measurements, vital signs, and ECG parameters will be summarized by treatment group at each of the protocol specified time points.

Further details will be provided in the trial's statistical analysis plan.

##### **12.5.1. Interim Safety Analysis/Study Stopping Rules**

An interim assessment of safety will be made by a study review group consisting of the Principal Investigator, the Galera Medical monitor, the CRO medical monitor, and other attendees as deemed appropriate. For this assessment, descriptive safety data will be reviewed after 15 patients have completed study treatment. In the event that any of the following occur, enrollment to the study will be suspended pending full review of all safety data to determine next steps:

- Radiation delay of  $\geq$  7 days in > 20 % of patients
- Chemotherapy delays of  $\geq$  7 days for non-hematologic toxicity, or discontinuation of chemotherapy for hematologic toxicities in >20% of patients.
- Progression of malignancy within 3 months of enrollment in > 20% of patients
- Discontinuation of treatment due to treatment-related AEs (GC4419 or chemoradiotherapy) within 3 months of enrollment  $\geq$  33% of patients.

Safety will be assessed on an on-going basis by the CRO Medical Monitor and Galera MM, who may call for an unscheduled safety review by the study review group at any time.

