## 1. SYNOPSIS

Name of Sponsor/Company: Galera Therapeutics, Inc.	
Name of Investigational Product: GC4419	
Name of Active Ingredient: GC4419 (avasopasem manganese) (Manganese (II)), is a water soluble, highly stable, low molecular weight manganese-containing macrocyclic complex whose activity mimics that of naturally occurring Superoxide Dismutase (SOD) enzymes.)	
Title of Study: A Phase 2a Open-Label Trial of the Effects of Intravenous GC4419 on the Incidence and Severity of Esophagitis in Subjects Receiving Chemoradiotherapy for Lung Cancer	
Number of Study Center(s): 10-15 centers in the United States	
Estimated Enrollment Period: 15-18 months	
Studied period (years): Estimated date first patient enrolled: December 2019 Estimated date last patient completed assessment for primary endpoint: December 2021	Phase of development: 2a
Objectives: Primary: 

To evaluate the incidence of acute radiation esophagitis (<math>\geq</math> Grade 2; National Cancer Institute-Common Terminology Criteria for Adverse Events [NCI-CTCAE] version 5) through the end of chemoradiotherapy for non-small cell lung cancer (NSCLC) and small cell lung cancer (SCLC) when GC4419 is added.

 Secondary: 

To evaluate and compare the incidence of acute severe (Grade 3-4) radiation esophagitis by NCI-CTCAE scales (Grade 3-4) through the completion of chemoradiotherapy;

To evaluate and compare the incidence of acute esophagitis <math>\geq</math> Grade 2, 4 weeks after completion of chemoradiotherapy, using the NCI-CTCAE scale;

To evaluate and compare the presence of acute severe radiation esophagitis 4 weeks after completion of chemoradiotherapy;

To evaluate the incidence of acute (through 90 days after radiation therapy) radiation pneumonitis, <math>\geq</math> Grade 2 using NCI-CTCAE scale;

To evaluate the adverse events (AEs) associated with GC4419 by the NCI-CTCAE scale;

To assess weight loss (percent weight change from baseline through the completion of chemoradiotherapy, and 4 weeks after treatment).

	

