**Statistical Considerations:**

The incidence of  $\geq$  Grade 2 esophagitis will be summarized and compared descriptively with historical controls based incidence rate of 30% incidence ([Fogh 2017](#), [Kwint 2012](#), [Palma 2013](#)) for chemoradiotherapy alone (range in literature since 2010; 18-42%). Percentages and 95% confidence intervals will be calculated and a binomial test performed.

A dropout/in evaluable rate of 10% is assumed, leading to an overall target enrollment of approximately 60 subjects to yield 55 who either complete treatment or are known to have had esophagitis before discontinuation.

For illustration, if the true incidence of  $\geq$  Grade 2 esophagitis in GC4419-treated subjects is 13%, the trial will have roughly 80% power with 55 subjects in the analysis to demonstrate incidence lower than 30% with a one-sided Type I error rate of 2.5%.

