## 12. STATISTICS

### 12.1. General Considerations

A separate statistical analysis plan will provide technical details of the statistical analyses to be performed, in addition to the specifications in this protocol.

All statistical analyses will be conducted with the SAS® software package version 9.2 or higher.

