### 12.3. Analysis Populations

The primary efficacy population will include all subjects who receive at least one dose of GC4419 and either a) complete their RT course or b) discontinue their RT course early but are known to have had acute radiation esophagitis. Sensitivity analyses will also be performed to assess the effect on estimated incidence when including GC4419-treated subjects who did not complete their RT course and did not have observed acute radiation esophagitis before discontinuing. Safety analyses will include all subjects who receive at least one dose of GC4419. Efficacy and safety may also be summarized for a “per protocol” population of subjects completing RT/chemotherapy and at least 5 weeks of GC4419.

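### Section 12.5.1: for full-course patients the 3-month progression window closes at least 22 days before the first scheduled tumor assessment, and the one scheduled look has an unclear trigger and denominator

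*Combined protocol and SAP*

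**What the plan says.** Section 12.5.1 sets one scheduled look by a study review group: "descriptive safety data will be reviewed after 15 patients have completed study treatment". The consequence is stated as "In the event that any of the following occur, enrollment to the study will be suspended pending full review of all safety data". Four criteria follow, on RT delay, chemotherapy delay or discontinuation, progression, and discontinuation for treatment-related AEs (33% or more within 3 months of enrollment). The progression criterion reads "Progression of malignancy within 3 months of enrollment in > 20% of patients". The section also provides for ongoing assessment by the two medical monitors, "who may call for an unscheduled safety review by the study review group at any time". It does not define completion of study treatment, the start of the enrollment clock, or the denominator.

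Section 12.3 says "Safety analyses will include all subjects who receive at least one dose of GC4419". Section 12.1 says "A separate statistical analysis plan will provide technical details of the statistical analyses to be performed"; that plan is not in the supplied text.

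On imaging, Sections 10.1.4, 10.8.1 and 10.8.2 and Appendix 1 place tumor assessments at screening, at 90 ± 15 days after the last RT day, and at 6, 9 and 12 months. Sections 10.1.3 and 10.7.5 separately require a chest CT, with contrast unless contraindicated, on the last RT day or at early termination, for pneumonitis. Section 11.2.4 has progression found by scan or clinical evaluation recorded on the CRF.

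**The concern.** Section 9.1 names interference with the anti-tumor effect of chemoradiotherapy as a potential risk, and there is no control arm. Progression is the only one of the four criteria that concerns tumor outcome. If no scheduled tumor assessment falls inside its window, the criterion depends on progression noticed clinically or on a scan taken for another purpose. With 15 patients, more than 20% means at least 4 (3/15 is exactly 20%), so one or two unrecorded progressions can decide the result.

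The trigger and denominator affect all four criteria. A look that waits for 15 completers comes later when more patients stop. If the denominator were completers only, the discontinuation criterion could hardly be met, because those who stopped study treatment would not be counted.

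**Working it through.** **Inputs.** RT of at least 60 Gy in fractions of 1.8-2.0 Gy, once daily on weekdays (6.2); about 30 and at most 35 doses (Synopsis); tumor visit 75-105 days after the last RT day (10.8.1); screening within 28 days of RT start (10.6); enrollment over 15-18 months (Synopsis); dropout: "A dropout/in evaluable rate of 10% is assumed". Assumed: enrollment 0-28 days before RT Day 1, a Monday start, no RT breaks, even accrual.

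**The plan's own treatment length.** 60/2.0 = 30 fractions. Thirty weekdays from a Monday end 39 days after RT Day 1, which is study Day 40. This matches the stated 6 weeks or so and the last dosing block (Days 36-40) in Appendix 1. Thirty-five fractions end 46 days after RT Day 1. A start on another weekday takes 41 days for 30 fractions and 48 for 35.

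**Gap for a full course.** Three calendar months are 89-92 days. Gap = lead + RT days + visit day − window.

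| Case | Gap in days |
|---|---|
| Smallest | 0 + 39 + 75 − 92 = 22 |
| Nominal 90-day visit | 0 + 39 + 90 − 92 = 37 |
| 35 fractions, earliest visit | 0 + 46 + 75 − 92 = 29 |
| 28-day lead, earliest visit | 28 + 39 + 75 − 92 = 50 |

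RT breaks widen the gap. A permitted weekend fraction could shift it by about a day.

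**Early stoppers.** The visit is counted from the last RT day. If RT stops 18-38 days after Day 1, the smallest gap is 1-21 days. At 17 days or sooner, the earliest visit is inside the window (17 + 75 = 92, enrollment on Day 1).

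**What falls inside the window.** The end-of-RT chest CT is 39 to 46 + 28 = 74 days from enrollment, so inside. The 4-week examination (28 ± 15 days after RT) is at 39 + 13 = 52 to 74 + 43 = 117 days, so only partly inside.

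**Window still open at the look.** Sixty subjects over 15 or 18 months is one per 7.6 or 9.1 days. The synopsis runs from a first patient in December 2019 to "Estimated date last patient completed assessment for primary endpoint: December 2021". Those 24 months, less 39-74 days of treatment, imply about 22 months of accrual, or one per 11.2 days. Take 3 months as 91 days. If nobody discontinues, the look comes 39-74 days after the 15th enrollment. Subject k has then been followed for (15 − k) × spacing + 39 to 74 days. If about 17 must be treated, 17 replaces 15.

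| Accrual | Of the first 15, at 91 days or more: no discontinuation | About 17 treated |
|---|---|---|
| 15 months | 8-12 | 10-14 |
| 18 months | 9-13 | 11-15 |
| 22 months | 10-13 | 12-15 |

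The 15th subject reaches 91 days 91 − 74 = 17 to 91 − 39 = 52 days after finishing treatment.

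**Trigger, read literally.** Expected number treated to give 15 completers = 15/(1 − d).

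| Discontinuation d | Treated | Delay at one per 7.6-11.2 days |
|---|---|---|
| 10% (plan) | 16.7 | 13-19 days |
| 33% (assumed) | 22.4 | 56-82 days |
| 50% (assumed) | 30.0 | 114-167 days |

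**The case against.** The strongest reply is that progression can be found and recorded inside the window. The end-of-RT chest CT lies there, physical examinations are done then and at 4 weeks, and Section 11.2.4 already sends progression found by any route to the CRF. The suspension clause can be read as a standing rule not tied to the scheduled look, and the monitors may convene a review at any time. This stands. A reader might infer that the rule cannot detect progression at all, and the documents do not support that. What remains is that no in-window scan is specified to be read for progression, and no second review or updated listing is scheduled.

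A reader might also take 22 days as the minimum for every patient. It is not, because early RT stoppers have a smaller gap or none.

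Nor do the two weaknesses simply add up. A later look gives the progression window more time to close: at an assumed 33% discontinuation the 56-82 day delay exceeds the 17-52 days needed, so all of the first 15 would have reached 3 months.

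The longer delays rest on assumed rates and a literal reading of completion. If the term covers patients who finished or stopped, the look does not move. The synopsis favors the literal reading, since it separates subjects who complete treatment from those with esophagitis before discontinuing, but 12.5.1 does not settle it.

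Finally, 12.3 points to all treated subjects as the denominator, and the separate analysis plan may say so. The rule that suspends enrollment is in the protocol, however, and should be clear there.

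**Conclusion.** The point holds as a minor design weakness. For patients given 30 or more weekday fractions without breaks, and enrolled no later than RT Day 1, the first assessment labelled as a tumor assessment falls at least 22 days after the progression window closes. The criterion therefore relies on incidental detection.

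At the only scheduled look the window is still open for some of the cohort: 8-13 of the first 15 have reached 3 months with no discontinuation, about 10-15 at the plan's 10%. Both ranges assume even accrual; at the top of the second, none of the 15 is still within the window.

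The trigger effect is small at the plan's own dropout (about 17 treated, 13-19 days later) and larger only at assumed higher rates. The documents do not support a claim that the look would in fact be months late. The unstated denominator needs a sentence however completion is read.

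**What to change.** In Section 12.5.1:

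- **Cohort and denominator.** Hold the review when the first 15 subjects given at least one dose of GC4419 have completed or permanently discontinued study treatment. Use those 15 as the denominator for all four criteria, consistent with 12.3.
- **Progression.** Reconcile the progression window with the imaging schedule, for example by having the end-of-RT chest CT that is already required also read and recorded for progression. Give the review group one updated progression listing once all 15 have reached 3 months from enrollment, and say from which date that clock runs.

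The window and threshold remain the sponsor's decision.

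The cost is a paragraph of wording, a recorded read of an existing scan, and one listing; no visit or scan is added. There are two drawbacks. The end-of-RT CT is an early read and may miss later progression. The new trigger brings the look earlier when patients discontinue, leaving less follow-up at that point, which the updated listing offsets.

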## **12.6. Primary Efficacy Analysis**

Incidence of acute radiation esophagitis ( $\geq$  Grade 2) will be presented descriptively along with 95% Clopper-Pearson exact confidence intervals. The incidence will be formally tested against 30% by a binomial test using the “exact binomial;” statement in SAS’s Frequency procedure (PROC FREQ).

### **12.6.1. Multiplicity**

Because the trial has only one primary endpoint and because the secondary endpoints are only descriptively presented, no accounting for multiple comparisons is planned.

### **12.6.2. Handling of Missing Data**

Investigators should make reasonable attempts to continue to collect Esophagitis RTOG and CTCAE scores for inclusion in the study database for subjects who discontinue from study drug but continue to receive further RT fractions.

The trial’s statistical analysis plan will discuss the imputation strategy for subjects who lack Esophagitis scores, who discontinue from the trial without complete follow-up of Esophagitis scores, and whose resolution date of severe Esophagitis is unknown.

## **12.7. Secondary Efficacy Analyses**

### **12.7.1. Incidence Endpoints**

Secondary incidence endpoints will be presented descriptively along with 95% Clopper-Pearson exact confidence intervals. Each incidence endpoint will have an analysis population that includes all subjects who receive at least one dose of GC4419 and either a) complete the follow-up period for the endpoint or b) discontinue follow-up early but are known to have had the endpoint.

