### 12.2. Sample Size

Approximately 60 subjects will be enrolled to ensure that 55 subjects are evaluable for the primary analysis, with an assumed proportion of early discontinuations without previous  $\geq$  Grade 2 esophagitis of approximately 10%.

The incidence of  $\geq$  Grade 2 esophagitis will be summarized and compared descriptively with historical controls based incidence rate of 30% for chemoradiotherapy alone ([Palma 2013](#), [Kwint 2012](#), [Fogh 2016](#)).

For illustration, with 55 patients in the primary analysis, the 95% Clopper-Pearson confidence interval around an observed incidence of  $\geq$  Grade 2 esophagitis (NCI-CTCAE) of 16% (9/55) would be 8% to 29%.

Assuming that the true incidence of  $\geq$  Grade 2 esophagitis in GC4419-treated subjects is 13%, the trial will have roughly 80% power with 55 subjects in the analysis to demonstrate incidence lower than 30% with a one-sided Type I error rate of 2.5%.

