#### 12.4.2. Secondary Efficacy Endpoints

- Incidence of acute severe (Grade 3-4) radiation esophagitis by the NCI-CTCAE scale (Grade 3-4) through the completion of chemoradiotherapy;

- Incidence of acute esophagitis  $\geq$  Grade 2 through 4 weeks after completion of chemoradiotherapy, using the NCI-CTCAE scale;
- Incidence of acute severe (Grade 3-4) radiation esophagitis through 4 weeks after completion of chemoradiotherapy;
- Presence of acute ( $\geq$  Grade 2) and acute severe (Grade 3-4) radiation esophagitis at evaluation 4 weeks after completion of chemoradiotherapy;
- Incidence of acute (through 90 days after radiation therapy) radiation pneumonitis,  $\geq$  Grade 2 by the NCI-CTCAE scale;
- Percentage weight change from baseline through the completion of chemoradiotherapy and 4 weeks after treatment.

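### For pneumonitis through 90 days, the secondary incidence rule keeps early leavers only if they had the event, and the protocol states no analysis that offsets this

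*Combined protocol and SAP*

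**What the plan says.** Section 12.7.1 sets the analysis population for every secondary incidence endpoint. A subject must have received at least one dose of GC4419 and must "either a) complete the follow-up period for the endpoint or b) discontinue follow-up early but are known to have had the endpoint". The same section gives the method: "Secondary incidence endpoints will be presented descriptively along with 95% Clopper-Pearson exact confidence intervals". Section 12.6.1 confirms that the secondary endpoints are descriptive and carry no multiplicity adjustment.

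Section 12.4.2 lists the endpoints. The one with the longest follow-up is "Incidence of acute (through 90 days after radiation therapy) radiation pneumonitis", at Grade 2 or higher. The list also has esophagitis incidences through 4 weeks after chemoradiotherapy, and the presence of esophagitis at the 4-week evaluation.

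Three other provisions bear on early leavers:

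- Section 12.3: "Sensitivity analyses will also be performed to assess the effect on estimated incidence" when treated subjects who stopped RT early without observed esophagitis are put back.
- Section 12.6.2: the SAP is to give an imputation strategy for missing or incomplete esophagitis scores.
- Sections 12.3 and 12.5: safety tables use all treated subjects. Under 11.5, however, routine AE collection ends with the 30-day follow-up period.

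None of these provides an analysis of pneumonitis through 90 days.

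**The concern.** Whether an early leaver enters the denominator depends on that subject's outcome. Someone who has pneumonitis and then leaves counts fully; someone who leaves without it disappears. The exact interval is then computed on the selected set, so it reflects sampling error but not the selection.

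This is a single-arm trial, so readers are likely to set its pneumonitis rate beside rates from elsewhere, even though the protocol names no benchmark. Section 4.2 lists lung among the tissues GC4419 might protect. An artefact in either direction could therefore hide a benefit or suggest one. Loss by 90 days also includes any loss during RT, so it cannot be smaller. The protocol restores event-free leavers for esophagitis but states no counterpart for its longest-followed incidence endpoint.

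**Working it through.** **Inputs from the protocol.** About 60 subjects enrolled for 55 evaluable: "Approximately 60 subjects will be enrolled to ensure that 55 subjects are evaluable for the primary analysis" (12.2). Dropout: "A dropout/in evaluable rate of 10% is assumed" (synopsis), stated for the primary analysis only. Pneumonitis is scheduled for assessment at the end of RT (10.7.5) and at 90 ± 15 days (10.8.1).

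**Assumed inputs.** The protocol gives no pneumonitis rate, no loss rate to 90 days and no risk for leavers. All three are varied below.

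**Step 1: the plan's own interval.** The Clopper-Pearson interval for 9/55 is 7.8% to 28.8%. Section 12.2 says "9/55) would be 8% to 29" percent, so the interval method reproduces.

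**Step 2: what the rule estimates.** Let p be the completers' risk, d the share who leave early, and q the probability that a leaver's event is seen before departure. Then

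expected estimate = [p(1 − d) + dq] / [(1 − d) + dq].

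**Step 3: leaving unrelated to risk.** Every subject has risk p, and half of a leaver's risk falls before departure, so q = p/2. This holds, for example, if departures and onsets are both spread evenly over follow-up. For p = 15%:

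- d = 10%: (0.1350 + 0.0075) / (0.9000 + 0.0075) = 0.1425/0.9075 = 15.7%
- d = 20%: (0.1200 + 0.0150) / (0.8000 + 0.0150) = 0.1350/0.8150 = 16.6%
- d = 30%: (0.1050 + 0.0225) / (0.7000 + 0.0225) = 0.1275/0.7225 = 17.6%

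For p = 20% the same formula gives 20.9%, 22.0% and 23.3%. If no leaver has the event before departure, q = 0 and the bias is zero.

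**Step 4: when the sign changes.** With E events seen, N treated and m event-free leavers, the rule reports E/(N − m). If a fraction r of those m go on to have the event, the truth is (E + mr)/N. The rule is too high exactly when r < E/(N − m), and too low when r exceeds it.

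Take completer risk 20%, 20% leavers, and a quarter of the leavers' risk seen before departure:

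- Leavers at twice the risk (40%, q = 10%): truth 0.16 + 0.08 = 24.0%; estimate 0.18/0.82 = 22.0%, which is 2.0 points too low.
- Leavers at three times the risk (60%, q = 15%): truth 0.16 + 0.12 = 28.0%; estimate 0.19/0.83 = 22.9%, which is 5.1 points too low.

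**Step 5: what all-treated bounds would show.** Illustration with 60 treated and 9 events seen:

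| Event-free leavers | Planned rule | Leavers as non-events | Leavers as events |
|---|---|---|---|
| 6 (10%) | 9/54 = 16.7% (7.9–29.3) | 9/60 = 15.0% (7.1–26.6) | 15/60 = 25.0% (14.7–37.9) |
| 12 (20%) | 9/48 = 18.8% (9.0–32.6) | 9/60 = 15.0% (7.1–26.6) | 21/60 = 35.0% (23.1–48.4) |

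The planned output would give the first result only.

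**Step 6: is the gap covered elsewhere?** For pneumonitis, not in the protocol. Section 12.3 restores subjects by RT completion and esophagitis status, and 12.6.2 names esophagitis scores only. The all-treated AE tables could show pneumonitis, but routine collection stops 30 days after the last treatment. For esophagitis through 4 weeks, 12.3 does not reach a subject who completes RT and then leaves; 12.6.2 may, but its content is deferred to the SAP.

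**The case against.** The strongest reply is that the effect is small, of uncertain sign, and in an endpoint that is never tested. At 10% leavers, the only loss rate stated anywhere, the shift from a true 15% is 0.7 points, while the exact interval for 9/60 is about 20 points wide. The pneumonitis objective in 5.2 is to evaluate, not to compare, and an upward bias would work against the drug. All of this stands and limits the weight of the point. It does not remove it: the 10% is not a 90-day figure, and neither the planned estimate nor its interval would show how much depends on the leavers.

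A second reply concerns a time-to-event estimate. With scheduled assessments only at the end of RT and around Day 90, onset after Day 30 may be known only as the visit at which it was found. This also stands, so a cumulative incidence should not be the sole replacement.

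Three stronger readings are tempting, and the protocol does not support them:

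- A reader might infer that every secondary incidence is overestimated. Step 4 shows that the direction depends on who leaves. For presence at the 4-week evaluation, clause (b) can hardly apply to someone who left before that visit, so that figure is in effect a complete-case one without the built-in inflation.
- A reader might infer that no secondary endpoint has a balancing analysis. The esophagitis endpoints have partial cover through 12.3 and 12.6.2.
- A reader might take completion of follow-up to mean reaching Day 90 exactly, so that event-free subjects seen on Days 75 to 89 are removed, which would inflate the rate far more. Section 10.8.1 allows the visit at 90 ± 15 days. A subject seen inside that window has made the planned visit and has not discontinued. The wording merits one clarifying sentence, but no bias should be computed from that reading.

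**Conclusion.** The point holds in a limited form. For pneumonitis through 90 days, and for post-RT leavers in the esophagitis incidences through 4 weeks, the denominator is selected on the outcome. If leaving is unrelated to risk and half of a leaver's risk precedes departure, the overstatement at a true 15% is 0.7, 1.6 and 2.6 points with 10%, 20% and 30% leavers. If leavers are at higher risk it can vanish or turn into understatement, by 2.0 to 5.1 points in the examples above. All these rates are assumptions.

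For pneumonitis the protocol states no analysis that would reveal either direction. That is a statement about the protocol only: section 12.1 defers technical detail to a separate SAP, which was not available and may already address it. The primary test is unaffected.

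**What to change.** In section 12.7.1, or in the SAP:

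1. Keep the planned figure, and add two all-treated estimates for each incidence measured through a time point: event-free early leavers counted as non-events, then as events. Give each a 95% Clopper-Pearson interval, and report the number of event-free leavers.
2. Where onset or detection dates allow, add a cumulative incidence on all treated subjects, with death without the event as a competing event (Aalen-Johansen) and a 95% interval. Say how an event first found at a visit is dated.
3. State that a visit inside its protocol window counts as completed follow-up.

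The first and third items need no new data, only a few lines of text. The costs are slightly more analysis, a wider reported range, and onset times after Day 30 that may be known only to the visit date. The sponsor should confirm what the CRF records on pneumonitis onset between Day 30 and Day 90 before relying on the second item.
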